2.3.1 Risk Assessment

- For the following potential risks of clinical significance, summary of data related to these risks, and corresponding mitigation strategies for the investigational product (IP), benralizumab, may be found in the Investigator's Brochure.Serious hypersensitivity reactions (including anaphylaxis) are identified risks of biologic therapy, including benralizumab. Anaphylaxis may be life-threatening. Risk minimization recommends a minimum of a 1-hour observation period at the clinical site following IP administration for the appearance of any acute drug reactions.
- Development of anti-drug antibodies (ADA) to benralizumab has been documented. Theoretical risks of developing ADA include decreased drug efficacy and hypersensitivity reactions. There was no apparent impact of ADA on overall benralizumab safety or efficacy in the phase 3 trials.
- Eosinophils are a prominent feature of the inflammatory response to helminthic parasitic infections. Therefore, there is a theoretical risk that prolonged eosinophil depletion may diminish the ability to defend against helminthic parasites. There were no reports of helminth infection in the phase 3 asthma exacerbation studies.
- Malignancies have been reported at a low incidence in the completed and ongoing studies of benralizumab. Eosinophils have been found in association with solid tumors, especially tumors of epithelial origin (breast and colon), and may play an active role in tumor defense by modulating host defenses, or may be a bystander effect. However, the cause and consequences (ie, pro-tumorigenic versus antitumorigenic) of eosinophil recruitment and accumulation into tumors are unclear (Jacobsen et al., 2012).
- Serious infections have been reported for benralizumab. The incidence of serious infections was similar across groups in the phase 3 asthma exacerbation studies. A relationship between eosinophil depletion and serious infection has not been established.
- Information regarding the use of benralizumab in pregnant and lactating women is currently missing. Appropriate risk minimization measures have been implemented in the study protocol (see Section 1.3, 5.2 and 7.1).

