7.1 Discontinuation of Study Intervention

It may be necessary for a participant to permanently discontinue study intervention. If study intervention is permanently discontinued, the participant will remain in the study to be evaluated for safety and, if he/she had completed the study procedures at Visit 1 and have had at least one dose of the study intervention, baseline measurements will also be evaluated.

If a participant discontinued study intervention, procedures for an Early Study Intervention Discontinuation (E/D) follow-up should be followed as described in the SoA. Refer to Table 1 for data to be collected at the time of discontinuation of study intervention and follow-up and for any further evaluations that need to be completed

Participants may be discontinued from IP in the following situations.

- Participant decision. The participant is at any time free to discontinue treatment, without prejudice to further treatment (see Section 7.2).
- An AE that is considered to jeopardize the safety of a participant participating in the study as judged by the Investigator or AstraZeneca.
- Positive pregnancy test at any time during the study (see Section 8.4.8 Pregnancy), or breastfeeding.
- Severe non-compliance with the CSP.
- Development of any study-specific criteria for discontinuation, including:
 - An anaphylactic reaction to the IP,
 - A helminth parasitic infestation requiring hospitalization,
 - An asthma-related event

- o requiring hospitalization for more than 24h or intubation,
- requiring OCS treatment after week 11 (see Section 8.3.1 for further details)
- Any new or recurrent malignancy, except non-melanoma skin cancers,
- -19
 - Moderate or severe disease at any time during the study period.
 - Mild disease with lower respiratory tract symptoms at any time during the study period.
 - Mild disease without lower respiratory tract symptoms may continue in the study at the investigator's discretion and visits rescheduled per Section 5.5.4.
 - Asymptomatic patients with COVID-19 positive test should not be discontinued and visits rescheduled per Section 5.5.4.

For details relating to dose modifications, see Section 6.6.

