8.1 Efficacy Assessments

8.1.1 Functional Respiratory Imaging (FRI)

Functional Respiratory Imaging (FRI) is a quantitative method to measure biological responses to therapeutic interventions through structural and functional parameters using high-resolution CT and computational fluid dynamics. All CT scanners used in this study must be at least a 64-slice scanner. For a helical scan, the scanner should be able to acquire at least 64 slices per rotation using a slice thickness of 0.625 mm or lower (collimation of

64 x 0.625 mm, 128 x 0.5 mm, 256 x 0.6 mm, etc.) using a tube voltage of 100kV. FRI analyses will be conducted by a central vendor who will provide further guidance on the CT scanner requirements, CT scan procedure and scanner-specific scanning protocol settings required for the current study in a separate manual and guidance document. Study team training will also be provided by the central vendor to all relevant study team members prior to study center activation. Clinical evaluation of CT scans should be done by the study team as per local practice, and any abnormality identified should be recorded as an AE in the eCRF.

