8.4.2 Follow-up of AEs and SAEs

Any AEs that are unresolved at the participant's last AE assessment or other assessment/visit as appropriate in the study are followed up by the investigator for as long as medically indicated, but without further recording in the eCRF. AstraZeneca retains the right to request additional information for any participant with ongoing AE(s)/SAE(s) at the end of the study, if judged necessary.

Adverse event variables

'The following variables will be collected for each AE;

- AE (verbatim)
- The date when the AE started and stopped
- Intensity of the AE
- Whether the AE is serious or not
- Investigator causality rating against the Investigational Product (yes or no)
- Action taken with regard to Investigational Product
- AE caused participant's withdrawal from study (yes or no)
- Treatment for AE
- Outcome
- Causality assessment in relation to study procedure (yes or no)

In addition, the following variables will be collected for SAEs:

- Date AE met criteria for SAE
- Date investigator became aware of SAE
- AE is serious due to
- Date of hospitalization
- Date of discharge
- Probable cause of death
- Date of death
- Autopsy performed
- Causality assessment in relation to study procedure(s)
- Causality assessment to other medication
- AE description

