9.4.3 Safety

Safety analyses will be performed using the safety analysis set. Adverse events will be coded using the most recent version of the Medical Dictionary for Regulatory Activities that will have been released for execution by the Sponsor/designee.

Safety data will be presented using descriptive statistics unless otherwise specified.

The AEs will be presented by system organ class and/or preferred term covering number and percentage of patients reporting at least 1 event and number of events where appropriate. An overview of AEs will present the number and percentage of patients with any AE, AEs with outcome of death, SAEs, and AEs leading to discontinuation of IP. Separate AE tables will be

provided taken into consideration relationship as assessed by the Investigator, intensity, seriousness, death, and events leading to discontinuation of IP. An additional table will present number and percentage of patients with the most common AEs.

Vital signs

Vital sign parameters will be presented for each treatment group. Summary statistics for continuous variables cover n, mean, SD, Min, Q1, median, Q3, and Max.

Details of vital sign analyses will be provided in the SAP.

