3.6 Safety Analyses

All safety variables will be summarized using the safety analysis set and data presented according to actual treatment received.

Safety data will be presented using descriptive statistics unless otherwise specified.

All safety measurements will use all available data for analyses, including data from unscheduled visits and repeated measurements.

The domain safety covers exposure, Adverse events (AEs), clinical laboratory, vital signs, and ECG results.

Tables and listings are provided for the safety set.

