3.6.2 Adverse Events

3.6.2.1 Definitions and Derivations

AEs are collected from the time of first dose of IP, throughout the treatment period and until Week 15 safety follow-up period is completed. AE causality is as determined by the reporting investigator. AEs with date of onset on or after the earliest first dose of any of the components of the combination should be considered to be treatment emergent.

AEs will be coded using the most recent version of MedDRA that will have been released for execution by the Sponsor/designee.

Multiple occurrences of an AE in the same participant will only be counted once overall considering start date as the first day of first occurrence and stop date the last day of the last occurrence.

In the case that, during the study, a participant has more than one episode of the same preferred term with different levels of intensity, then the maximum intensity level will be used. The following ordering will be used to define maximum intensity level: Mild < Moderate < Severe.

For each participant and each AE, the worst severity recorded will be attributed and used in the by-severity summaries. Similarly, the worst causality (most related to study intervention) will be attributed and used in the by-causality summaries. If severity or causality is missing, a conservative approach for AE assessment (taking into account the worst case) will be followed.

Any AEs with incomplete start and end dates/times will be treated as follows:

- AEs with unknown start times, but with start date known, will be imputed with a time of 00:00, unless the start date corresponds to any given dosing date. In this case the start time will be imputed with the time of dosing. If this results in a start date/time after end date/time of the AE, then the time will also be imputed with 00:00.
- AEs with completely unknown start dates will be imputed with the date and time of dosing unless the end date is known and prior to dosing; in that case the start date will be imputed as the date of screening and a time of 00:00.
- AEs with partially known start dates/times will be treated as follows:

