3.6.2.2 Presentation

The AEs will be presented by SOC and/or preferred term covering number and percentage of participants reporting at least 1 event and number of events where appropriate. An overview of AEs will present the number and percentage of participants with any AE, AEs with an outcome of death, Serious adverse events (SAEs), and AEs leading to discontinuation of study intervention. Separate AE tables will be provided taking into consideration the relationship to study intervention as assessed by the Investigator, intensity, seriousness, death, and events leading to discontinuation of study intervention.

AE summaries will be ordered by the international order for SOC and by decreasing frequency for preferred term within SOC.

All reported AEs will be listed along with the date of onset, date of resolution (if AE is resolved), Investigator's assessment of intensity, whether the AE is serious or not, outcome, action taken with study intervention, and possible relationship to study intervention. A by-participant listing of all AE (including AEs before first dose of study intervention) will be provided. This listing will include the following information: study period, verbatim term, MedDRA SOC and preferred term, start date/time, end date/time, time from last dose, intensity, causality, action taken, whether the AE was classified as serious, the outcome of

the AE and the concomitant or additional treatment given, if any. Any AE occurring before the first dose of study intervention and/or the AE assessments that are unresolved at the participant's last assessment in the study will be included in the data listings but will not be included in the summary tables of AEs.

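### SAP 3.6.2.2 leaves adverse events still unresolved at the last assessment out of the AE summary tables, so ongoing post-dose AEs and SAEs are only listed and the tabulated incidence can only be too low

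*SAP*

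**What the plan says.** The last sentence of SAP 3.6.2.2 names two groups of AEs, joined by and/or: those occurring before the first dose, and those still open at the "last assessment in the study will be included in the data listings but will not be included in the summary tables of AEs". Either condition is enough to keep an event out of the tables.

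Other text on the same tables sets no such condition:

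- Protocol 9.4.3: "An overview of AEs will present the number and percentage of patients with any AE", followed by fatal AEs, SAEs and AEs leading to discontinuation of the product. It adds tables by system organ class and preferred term, relationship, intensity and seriousness. The opening paragraph of SAP 3.6.2.2 repeats nearly all of this.
- SAP 3.6.2.1: "AEs with date of onset on or after the earliest first dose" are treatment emergent. Resolution plays no part in the definition.
- Protocol 8.4.2: AEs unresolved at the last assessment are "followed up by the investigator for as long as medically indicated, but without further recording in the eCRF".

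The SAP Addendum (version 3.0) changes several safety outputs. Section 2.12 restores vital-sign summary tables because the SAP had departed from the protocol, and section 2.13 drops some listings. Nothing visible in it touches the AE rule.

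**The concern.** Excluding pre-dose events from treatment-emergent tables is normal practice. Excluding post-dose events because they have not yet ended is not. It selects on outcome, and it removes persistent events more often than short ones.

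Two examples from the protocol show what could go missing:

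- **Malignancy.** Protocol 2.3.1 notes that "Malignancies have been reported at a low incidence in the completed and ongoing studies of benralizumab". Section 7.1 lists "Any new or recurrent malignancy, except non-melanoma skin cancers" among the reasons to stop treatment, and Appendix C 2 says malignant tumours should generally be assessed as serious. A new malignancy still open at last contact would be absent from the AE, SAE and discontinuation tables.
- **CT findings at Visit 4.** Protocol 8.1.1 says that "any abnormality identified should be recorded as an AE in the eCRF". Visit 5 follows two weeks later, give or take 7 days, so a finding first recorded at Visit 4 has 7 to 21 days to resolve before it is excluded.

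The study has one arm and no Data Monitoring Committee. The AE tables are its summary statement of safety, and no comparator arm would share the same undercount.

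**Working it through.** **Step 1: what the rule does.** The plan states no figure to reproduce, so the first check compares the texts. Take an AE with onset after first dose that is unresolved at Visit 5, or at the early-discontinuation visit.

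- Under SAP 3.6.2.1 it is treatment emergent.
- Under Protocol 9.4.3 and the opening of SAP 3.6.2.2 it counts in the tables.
- Under the last sentence of SAP 3.6.2.2 it does not.

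These cannot all hold. The phrase about AE assessments being unresolved is loose, but the only workable meaning is AEs not resolved at last contact. The and/or rules out a reading limited to pre-dose events.

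**Step 2: does it correct itself?** Under Protocol 8.4.2 later follow-up is not recorded in the eCRF, so an open event will normally still be open in the analysis data.

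**Step 3: direction.** The rule only removes events. Each tabulated count is therefore at or below the full count, and equals it only if no removed event would have added to that row.

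**Step 4: one participant.** The safety set is everyone with at least one dose. Its size is assumed to lie between the planned 34 evaluable and 38 enrolled (Protocol synopsis). If one participant's only SAE is open at last assessment, the SAE percentage falls by

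- 1/38 = 2.6 points, up to
- 1/34 = 2.9 points.

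**Step 5: share of events dropped.** Week 0 to week 15 is T = 15 × 7 = 105 days. Assume onset uniform over T and exponential durations with mean D. The share still open at T is (D/T)(1 − exp(−T/D)):

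- D = 7: (7/105)(1 − exp(−15)) = 6.7%
- D = 14: (14/105)(1 − exp(−7.5)) = 13.3%
- D = 30: (30/105)(1 − exp(−3.5)) = 27.7%

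A simulation of 1,000,000 events gave the same three values.

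**Step 6: the row for participants with any AE.** Let p be the share of participants with a treatment-emergent AE, and q the share of those whose AEs are all open at last assessment. The tabulated percentage is p(1 − q). Both inputs are assumed:

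- p = 40%, q = 5% to 30%: 38% down to 28%
- p = 60%, q = 5% to 30%: 57% down to 42%
- p = 80%, q = 5% to 30%: 76% down to 56%

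The chance that at least one participant is lost from this row is 1 − (1 − pq)^N. With p = 40% and q = 5% it is 54% for N = 38 and 50% for N = 34. With p = 60% and q = 10% it is 90% and 88%.

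**The case against.** The strongest defence is that nothing is hidden. Every AE is listed with seriousness, outcome and action taken, the study plans about 38 participants, and SAE reporting to the sponsor runs separately. That stands as a limit on the harm: listings and expedited reporting are unaffected. It does not rescue the tables, which are what the protocol promises and what a report will quote.

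A reader might infer more than the documents support in five ways:

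- **That 7% to 28% is the fall in the participant percentages.** It is a share of events. A participant with another, resolved AE stays in the row for any AE, and fatal AEs have an outcome and are probably unaffected. The exposed rows are mainly organ class and preferred term, SAE, intensity, causality and discontinuation.
- **That the loss in the discontinuation table can be sized.** It depends on the time from onset to the early-discontinuation visit. The schedule gives a window of ±7 days with no stated anchor, so any single figure would rest on a chosen gap.
- **That the record can never be corrected.** Protocol 8.4.2 lets the sponsor request further information on ongoing events, and 8.4.7 requires updated SAE data within 24 hours of its being available. Events will normally stay unresolved in the data, but not necessarily always.
- **That SAP 3.6 flatly forbids the exclusion.** It says "All safety measurements will use all available data for analyses, including data from unscheduled visits and repeated measurements". In context this most naturally governs which measurements are used, against SAP 2.3.3, which keeps unscheduled post-baseline data out of summary tables. It is weak support and the point does not need it.
- **That the protocol's differing text on whether a participant who stops treatment stays in the study (Sections 7, 7.1 and 8.3.1) is part of the same fault.** It has almost no bearing on these tables. Rewording 7.1 towards withdrawal could cost a participant with three doses the Visit 5 contact, so this point gives no reason to change it.

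**Conclusion.** The rule is wrong as written. It conflicts with the SAP's own definition of treatment emergence, with the opening of the same SAP section and with Protocol 9.4.3, and the Addendum leaves it in place. The finding itself rests on the text alone and needs no assumption.

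The direction of the bias is certain, but its size is not known. It is zero only if no post-dose AE is open at any participant's last assessment. The figures in the working are illustrations. The per-participant figure assumes a safety set of 34 to 38, the event shares assume uniform onset and exponential durations, and the any-AE percentages assume p and q.

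This should be corrected because it affects the reported safety incidence. It does not affect participant protection or any efficacy result.

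**What to change.** Replace the last sentence of SAP 3.6.2.2, for example through a further item in section 2 of the Addendum, with:

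*AEs with onset before the first dose of study intervention will be listed only. All AEs with onset on or after the first dose will be included in the summary tables whatever their resolution status; those unresolved at the last assessment will be shown with outcome 'not resolved'.*

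The cost is one sentence and the matching selection condition in the AE table programs. Outcome is already collected for every AE (Protocol 8.4.2), so no new data, visits, calls or scans are needed, and the protocol does not change.

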3.6.3 Clinical Laboratory, Blood Sample

3.6.3.1 Definitions and Derivations

Laboratory tests that will be performed and analysed are reported in Table 11.

Table 11Laboratory Safety Variables

Haematology (Whole Blood)	Clinical Chemistry (Serum or Plasma)
Hemoglobin (Hb)	Alkaline phosphatase (ALP)
Leukocyte count	Alanine transaminase (ALT)
Leukocyte differential count (absolute count; including eosinophil absolute count)	Aspartate transaminase (AST)
Platelet count	Bilirubin, total
Potassium	Creatinine
Sodium	Glucose

3.6.3.2 Presentations

Laboratory values at screening will be listed by participant.

All values outside the clinical reference ranges will be flagged in the data listings. The abnormal values will be flagged with 'L' for values below the lower limit of the clinical reference range and 'H' for values above the upper limit of the clinical reference range and included in the listings. The Investigator will assess whether the values outside the clinical reference range are clinically significant. Clinically significant laboratory values will be recorded by the Investigator as AEs.

Descriptive statistics (for clinical chemistry, haematology) will be reported for both measures values (N, mean, SD, median, minimum, and maximum) .

Additional listings will be presented for urine pregnancy testing, reporting the sampling date and the result (Negative or Positive) for the Pregnancy (Serum or Urine) test.

Clinical laboratory data will be reported in System International units in the CSR.

3.6.4 Clinical Laboratory, Urinalysis

3.6.4.1 Definitions and Derivations

Not applicable.

3.6.5 Other Laboratory Evaluations

3.6.5.1 Definitions and Derivations

Not applicable.

3.6.5.2 Presentations

Not applicable.

3.6.6 Vital Signs

3.6.6.1 Definitions and Derivations

Vital sign parameters include systolic and diastolic blood pressure and heart rate.

3.6.6.2 Presentations

Vital signs data will be listed by participant and timepoint including the date/time of the assessment.

3.6.7 Electrocardiogram

3.6.7.1 Definitions and Derivations

An ECG will be performed at screening to access eligibility for the study.

3.6.7.2 Presentations

ECG data will be listed by participant, including ECG date, interpretation, details for abnormal ECG and clinical significance. ECG data will be summarized as baseline data.

3.6.8 Other Safety Assessments

Not applicable.

6 APPENDIX

6.1 Schedule of Activities

Activities	Before Screening	Screeni	Inte [We	erventi eeks]	on per	iod	E/D	Follow- up Week 15ª	Follow- 1p Week 15ª			
	Streeming	5	0	4	8	13				Details in CSP		
Visit	N/A	0	1	2	3	4	N/A	5	Notes	Section or Appendix		
Visit window (days) ^b	-30 to -1 before V0	-21 before V1	0	±5	±5	±5	±7	±7		Appendix		
General procedures:												
Informed consent	х									Section 5.1		
Provide instructions for medication withhold for screening, Visit 1 and 4	x	x			x				Instructions to adequately withhold maintenance and rescue asthma medications prior to Visit 1 and 4.	Section 8.1.1 and 8.1.2		
Past and current medical/surgical and asthma history (includes history of COVID-19 infections)		x							Substances: Drugs, alcohol, tobacco, e- cigarettes and marijuana	Section 5.1 and 5.2.1		
COVID-19 vaccination status		х								Section 5.1		
Medication status for asthma treatment		х				x				Section 5.1 and 5.2.1		
Inclusion and exclusion criteria (including smoking status)		x								Section 5.1 and 5.2.1		

Activities	Before Screen	Scree	Inte [We	erventi eeks]	on per	iod	E/D	Follow- up Week 15ª		
	ing	ling	0	4	8	13		15		Details in
Visit	N/A	0	1	2	3	4	N/A	5	Notes	CSP Section or
Visit window (days) ^b	-30 to - 1 before V0	-21 befor e V1	0	±5	±5	±5	±7	±7		Appendix
General procedures (continued):										

STATISTICAL ANALYSIS PLAN

D3250R00107 - ed. 2.0

Review exacerbations status and current medication for exclusion criteria			x						Section 5.2.2
Demography		х							Section 5.1
Height and weight		х							
12-lead ECG		х							Section 8.2.3
Laboratory assessments:	Laboratory assessments:								
COVID-19 test ^c	Before a	Before any visits or procedures as per prevailing local guidelines for COVID-19 testing						Section 5.1, 5.2.1, 5.5.4 and 8.2.5	
Clinical laboratory assessments (including blood eosinophils)		х							Section 8.2.4
Serum pregnancy test (WOCBP only)		x							Section 5.1, 5.2.1, 8.2.4.1 and 8.4.8
FSH (women < 50 years)		x							Section 5.1, 5.2.1 and 8.2.4.1

STATISTICAL ANALYSIS PLAN D3250R00107 - ed. 2.0

AstraZeneca 16-Feb-2024

Procedure	Before Scree	Scree	In	terven	tion po [W	eriod eeks]	E/	Follo w-up		
	ning	ning	0	4	8	13	D	Wee k 15ª		
Visit	N/A	0	1	2	3	4	N/ A	5	Notes	Details in CSP Section or Appendix
Visit window (days) ^b	-30 to -1 before V0	-21 before V1	0	±5	±5	±5	±7	±7		
Laboratory assessments (conti	nued):			•	-					
Urine pregnancy test (WOCBP only)			x d	_x d	хd	хd			For Visit 1 and 4, pregnancy status must be checked before CT scan. A positive urine test result must be confirmed with a serum pregnancy test.	Section 5.1, 5.2.1, 8.2.4.1 and 8.4.8
Safety assessments:	Safety assessments:									
Physical examination		х	x	x	x	x	x			Section 8.2.1 and 8.4.5
Adverse Events (AE) ^e		x	x	x	x	x	x	x	AEs should be reported from first dose of treatment to end of study. SAEs should be reported from signing of ICF.	Section 8.4
History of asthma exacerbation ^e	х	х	x	x	x	x	x	х		Section 8.3 and 8.4.6
Asthma Medication (maintenance and rescue)		x	x	x	x	x	x	x	Oral corticosteroids should also be documented in the eCRF.	Section 5.2.1 and 6.5
Concomitant medication		х				x		х		Section 5.2.1 and 6.5
Vital signs		х					х			Section 8.2.2
Procedure	Before Scree ning	Scree ning	In	terven 4	tion po [Wo	eriod eeks]	E/ D	Follo w-up Wee		
Visit	N/A	0	1	2	3	4	N/ A	5	Notes	Details in CSP Section or Appendix
Visit window (days) ^b	-30 to -1 before V0	-21 before V1	0	±5	±5	±5	±7	±7		
Patient Reported Outcomes As	ssessment	s:								

CC

STATISTICAL ANALYSIS PLAN D3250R00107 - ed. 2.0

FRI assessment:										
CT scan h,i, j,k			x			x			A urine pregnancy test should be done prior to all CT scan procedures.	Section 8.1.1
Lung function assessments:										
Spirometry with reversibility test post- BD (if needed) ^{k,1}		х								Section 5.1 and 8.1.2
Spirometry (pre- bronchodilator) ^{k,m}			x			x			Spirometry should be done after CT scan procedure.	Section 8.1.2
Investigational Product	Investigational Product administration:									
Study intervention			Xn	Χn	Χn					Section 6.2

^a Only for participants who completed 3 doses of study intervention.

- ^b Any rescheduling of visits beyond the visit window indicated in this Schedule of Activity should be an exception and the reason should be recorded in the ISF.
- ^c Each investigator site shall follow prevailing local guidelines for COVID-19 testing before any visits or procedures. Participants are considered as having positive COVID-19 test when they fulfill the criteria defined as per aforementioned guidelines. If a participant presents with a positive COVID-19 test result, Visit 0 may be rescheduled as per guidance in Section 5.4 of the CSP. If a participant presents with a positive COVID-19 test result at any time, visits may be rescheduled as per guidance in Section 5.5.4 of the CSP.
- ^d A urine pregnancy test must be done before all study assessments (PROs, CT scan and spirometry test). All study assessments and administration of benralizumab must be stopped if a participant has a positive urine pregnancy test.
- ^e If a participant experiences an acute exacerbation or respiratory tract infection during the study, refer to Section 8.3 of the CSP for further details.

f	CCI
g	

- ^h CT scans should be conducted using the low radiation dose scanning protocol as approved by the central vendor during the certification process for the CT scanning procedures prior to study center activation for the study.
- ⁱ CT scans will be taken at two breathing levels: TLC and FRC.
- ^j All CT scans will be conducted with respiratory gating using equipment (CE-marked) provided by the central vendor.

STATISTICAL ANALYSIS PLAN

- $D3250R00107-ed.\ 2.0$
- ^k Maintenance and rescue asthma medications need to be adequately withheld prior to Visit 0, 1 and 4 for the spirometry testing and/or CT procedures that will be scheduled during these visits (see Section 8.1.1 of the CSP for CT scan procedures and Section 8.1.2 of the CSP for spirometry procedures).
- Reversibility testing should be conducted if participants do not have historical documentation (medical records) of reversibility post-BD. Participants will need either documented reversibility post-BD either historically (medical records) or at screening visit to fulfil inclusion criterion 2 (see Section 5.1 of the CSP).
- ^m Spirometry test conducted during Visit 1 and 4 should always be performed after the participants undergo the CT scan procedure. If not feasible, there should be at least 30 minutes between the spirometry test and subsequent CT scan procedure.
- ⁿ For WOCBP only, study intervention should only be administered after confirmation with a negative urine pregnancy test.

6.2 **Prednisone Equivalent Doses**

The following table gives an overview of prednisone equivalent doses (eg 50 mg cortisone is equivalent to 10 mg prednisone) and should be used for converting non-prednisone medications to prednisone equivalent. Multiply the dose of the OCS taken by the subject (in milligrams) in the first column by the conversion factor in the final column to get the equivalent dose of prednisone (in milligrams).

For example: Subject is taking 16 mg of methylprednisolone once daily. To convert to prednisone: 16 mg methylprednisolone $\times 5/4 = 20$ mg prednisone. 16 mg of methylprednisolone once daily is equivalent to 20 mg of prednisone once daily.

Medication preferred	Equivalent	Conversion factor for
term	dose	converting to an equivalent
		prednisone dose
Prednisone	10 mg	1
Prednisone acetate	10 mg	1
Cortisone	50 mg	1/5
Hydrocortisone	40 mg	1/4
Methylprednisolone	8 mg	5/4
Prednisolone	10 mg	1
Triamcinolone	8 mg	5/4
Betamethasone	1.2 mg	25/3
Dexamethasone	1.5 mg	25/4
Budesonide*	2.25 mg	10/9
Deflazacort*	12 mg	5/6

*equivalent doses and conversion factors based on TULIP study. All others based on information from https://clincalc.com/Corticosteroids/#1 and the following references:

1. Chrousos GP, "Chapter 39. Adrenocorticosteroids & Adrenocortical Antagonists" (Chapter). Katzung BG, Masters SB, Trevor AJ: Basic & Clinical Pharmacology, 11e.

2. Asare K. Diagnosis and treatment of adrenal insufficiency in the critically ill patient. Pharmacotherapy. 2007;27(11):1512-28. PMID 17963461.

3. Glucocorticoids. Facts and Comparisons 4.0. Wolters Kluwer Health, Inc. Conshohocken, PA.

4. Schimmer BP, Funder JW, "Chapter 42. ACTH, Adrenal Steroids, and Pharmacology of the Adrenal Cortex" (Chapter). Brunton LL, Chabner BA, Knollmann BC: Goodman & Gilman's The Pharmacological Basis of Therapeutics, 12e.

Approval Signatures

Document Name:	Statistical Analysis Plan 04 Jun 2024 D3250R00107
Document Number:	VV-TMF-7011617
Parexel Version Number:	
System Version Number:	2.0

Document Approvals	
Reason for signing: Approved	Name: PPD Role: PPD Date of signature: PPD

Developed from TP-BPM-WW-032; related to SOP-BPM-WW-001 D3250R00107

Statistical Analysis Plan Addendum

AstraZeneca

D3250R00107

BURAN: Effects of BenralizUmab on AiRwAy DyNamics inSevere Eosinophilic Asthma using Functional RespiratoryImaging Parameters

Statistical Analysis Plan Addendum

Parexel Project Number: 264960

Developed from TP-BPM-WW-032; related to SOP-BPM-WW-001 D3250R00107

Statistical Analysis Plan Addendum

SPONSOR SIGNATURE PAGE

	Signatory
Review/Approval	PPD
	PPD

Developed from TP-BPM-WW-032; related to SOP-BPM-WW-001 D3250R00107

Parexel Signature Page

Signature(s) below confirm that the Statistical Analysis Plan Addendum was developed in accordance with SOP-GDO-WW-019 and that it is approved for release.

